12.2 Reporting of adverse events

All events meeting the definition of an AE must be collected and reported. This includes events from the first trial-related activity after the patient has signed the informed consent until visit 16 (end of treatment) for patients enrolling into a subsequent trial with concizumab and at the end of the post-treatment follow-up period (visit 17) for patients not enrolling in to a new trial. The events must be recorded in the applicable eCRF forms in a timely manner; see timelines below in [Figure 12-1](#)

During each contact with the trial site staff, the patient must be asked about AEs and technical complaints, for example by asking: “Have you experienced any problems since the last contact?”

All AEs, either observed by the investigator or patient, must be reported by the investigator and evaluated. All AEs must be recorded by the investigator on an AE form. The investigator should report the diagnosis, if available. If no diagnosis is available, the investigator should record each sign and symptom as individual AEs using separate AE forms.

For SAEs, a safety information form must be completed in addition to the AE form. If several symptoms or diagnoses occur as part of the same clinical picture, one safety information form can be used to describe all the SAEs.

Protocol
Trial ID:NN7415-4255
UTN:U1111-1179-3872
EudraCT no.:2016-000614-29

~~CONFIDENTIAL~~

Date:	28 August 2018	Novo Nordisk
Version:	5.0	
Status:	Final	
Page:	89 of 127	

AESIs regardless of the seriousness, must be reported using the AE form and safety information form

For all non-serious AEs, the applicable forms should be signed when the event is resolved or at the end of the trial at the latest.

Timelines for initial reporting of AEs:

The investigator must complete the following forms in the case report form (CRF)/eCRF within the specified timelines:

- **SAEs:** The AE form **within 24 hours** and the safety information form **within 5 calendar days** of the investigator's first knowledge of the SAE.

Both forms must be signed within 7 calendar days from the date the information was entered in the eCRF.

For SAEs requiring reporting on a specific event form: In addition to the above the specific event form within **14 calendar days** from the investigator's first knowledge of the AE.

- **Non-serious AEs fulfilling the AESI criteria:** The AE form and safety information form **within 14 calendar days** of the investigator's first knowledge of the event.

If the eCRF is unavailable, the concerned AE information must be reported on a paper AE form and sent to Novo Nordisk by fax, e-mail or courier within the same timelines as stated above. When the eCRF becomes available again, the investigator must enter the information on the form into the eCRF.

[figure not shown]
Protocol
 Trial ID:NN7415-4255
 UTN:U1111-1179-3872
 EudraCT no.:2016-000614-29

~~CONFIDENTIAL~~

Date: 28 August 2018
 Version: 5.0
 Status: Final
 Page: 90 of 127

Novo Nordisk

Contact details (fax, telephone, e-mail and address) are provided in the investigator trial master file.

Timelines are for the completion of forms from the time of investigator's awareness
 AEs requiring specific event forms are described in Section 12.1.5 and 12.1.6

AE: Adverse event **AESI:** Adverse event of special interest **SIF:** Safety information form

Figure 12–1 Reporting of AEs

Novo Nordisk assessment of AE expectedness:

Novo Nordisk assessment of expectedness is performed according to the following reference documents: Investigator's Brochure; Current version and any updates thereto.

Reporting of trial product-related SUSARs by Novo Nordisk:

Novo Nordisk will notify the investigator of trial product-related suspected unexpected serious adverse reactions (SUSARs) in accordance with local requirements and ICH GCP¹. In addition, the investigator will be informed of any trial-related SAEs that may warrant a change in any trial procedure.

In accordance with regulatory requirements, Novo Nordisk will inform the regulatory authorities, including EMA, of trial product-related SUSARs. In addition, Novo Nordisk will inform the International Review Boards/Independent Ethics Committees (IRBs/IECs) of trial product-related SUSARs in accordance with local requirement and ICH GCP¹, unless locally this is an obligation of the investigator.

Protocol
 Trial ID:NN7415-4255
 UTN:U1111-1179-3872
 EudraCT no.:2016-000614-29

~~CONFIDENTIAL~~

Date:	28 August 2018	Novo Nordisk
Version:	5.0	
Status:	Final	
Page:	91 of 127	

Novo Nordisk products used as concomitant medication or non-investigational medicinal product:

If an AE is considered to have a causal relationship with a Novo Nordisk marketed product used as non-investigational medicinal product rFVIII (turoctocog alfa) *or* concomitant medication in the trial, it is important that the suspected relationship is reported to Novo Nordisk, e.g. in the alternative aetiology section on the safety information form. Novo Nordisk may need to report this adverse event to relevant regulatory authorities.

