12.1.2 Serious adverse event

A serious adverse event (SAE) is an experience that at any dose results in any of the following:

- Death.
- A life-threatening^a experience.
- In-patient hospitalisation^b or prolongation of existing hospitalisation.
- A persistent or significant disability or incapacity^c.
- A congenital anomaly or birth defect.
- Important medical events that may not result in death, be life threatening^a or require hospitalisation^b may be considered an SAE when - based on appropriate medical judgement - they may jeopardise the patient and may require medical or surgical intervention to prevent one of the outcomes listed in the definition of SAE^d.

^a. The term “life threatening” in the definition of SAE refers to an event in which the patient was at risk of death at the time of the event. It does not refer to an event which hypothetically might have caused death if it was more severe.

^b. The term “hospitalisation” is used when a patient:

- Is admitted to a hospital or in-patient, irrespective of the duration of physical stay, or
- Stays at the hospital for treatment or observation for more than 24 hours

Protocol
 Trial ID:NN7415-4255
 UTN:U1111-1179-3872
 EudraCT no.:2016-000614-29

~~CONFIDENTIAL~~

Date:	28 August 2018	Novo Nordisk
Version:	5.0	
Status:	Final	
Page:	82 of 127	

Medical judgement must always be exercised, and when in doubt, the hospital contact should be regarded as a hospitalisation. Hospitalisations for administrative, trial related and social purposes do not constitute AEs and should therefore not be reported as AEs or SAEs. Hospital admissions for surgical procedures, planned before trial inclusion, are not considered AEs or SAEs.

^cA substantial disruption of a patient's ability to conduct normal life functions (e.g. following the event or clinical investigation the patient has significant, persistent or permanent change, impairment, damage or disruption in his body function or structure, physical activity and/or quality of life).

^d For example intensive treatment in an emergency room or at home of allergic bronchospasm, blood dyscrasia or convulsions that do not result in hospitalisation or development of drug dependency or drug abuse.

The following adverse events must always be reported as an SAE using the important medical event criterion if no other seriousness criteria are applicable:

- Suspicion of transmission of infectious agents via the trial product

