12.1.6 Adverse event of special interest

An adverse event of special interest (AESI) is an event, which in the evaluation of safety, has a special focus. In this trial, the following AEs fulfil the AESI criteria:

- Thromboembolic events including but not limited to,
 - disseminated intravascular coagulation (DIC) (A),
 - clinical signs or laboratory indications of arterial and venous thrombosis including myocardial infarction (B),
 - pulmonary embolism (C),
 - stroke (D),
 - deep vein thrombosis (E),
 - other clinically significant thromboembolic events (F) and peripheral artery occlusion (see below G), see definitions below.

The AESIs must be reported on an AE form and a safety information form.

Protocol
 Trial ID:NN7415-4255
 UTN:U1111-1179-3872
 EudraCT no.:2016-000614-29

~~CONFIDENTIAL~~

Date: 28 August 2018
 Version: 5.0
 Status: Final
 Page: 85 of 127

Novo Nordisk

A) Definition of disseminated intravascular coagulation (DIC), as defined below:

The definition of DIC in this trial should be made according to the International Society on Thrombosis and Haemostasis (ISTH) criteria. Thus, a DIC diagnosis may be based on clinical signs and symptoms of a bleeding tendency or thrombotic tendency, organ dysfunction and the laboratory parameters criteria as listed below:

- Platelet count ($>100 \times 10^9/L = 0$, $<100 \times 10^9/L = 1$, $<50 \times 10^9/L = 2$)
- Elevated D-dimer (no increase = 0, moderate increase = 2, strong increase = 3)
- Prolonged PT ($<3 \text{ s} = 0$, $>3 \text{ but } <6 \text{ s} = 1$, $>6 \text{ s} = 2$)
- Fibrinogen level ($>1 \text{ g/L} = 0$, $<1 \text{ g/L} = 1$)
- Calculate score: ≥ 5 compatible with overt DIC

(B) Myocardial infarction is defined according to the “Third Universal Definition of Myocardial Infarction”²⁴

Criteria for acute myocardial infarction - The term acute myocardial infarction (MI) should be used when there is evidence of myocardial necrosis in a clinical setting consistent with acute myocardial ischemia. Under these conditions any one of the following criteria meets the diagnosis for MI:

- Detection of a rise and/or fall of cardiac biomarker values [preferably cardiac troponin (cTn)] with at least one value above the 99th percentile upper reference limit (URL) and with at least one of the following:
 - Symptoms of ischemia.
 - New or presumed new significant ST-segment–T wave (ST–T) changes or new left bundle branch block (LBBB).
 - Development of pathological Q waves in the ECG.

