- 2. clinical evidence of cerebral, spinal cord, or retinal focal ischemic injury based on symptoms persisting 24 hours or until death, and other etiologies excluded.

Note: CNS infarction includes haemorrhagic infarctions, types I and II; see “Haemorrhagic Infarction”.

Definition of ischemic stroke: An episode of neurological dysfunction caused by focal cerebral, spinal, or retinal infarction. Note: Evidence of CNS infarction is defined above.

Definition of silent CNS infarction: Imaging or neuropathological evidence of CNS infarction, without a history of acute neurological dysfunction attributable to the lesion.

Definition of intracerebral haemorrhage: A focal collection of blood within the brain parenchyma or ventricular system that is not caused by trauma. Note: Intracerebral haemorrhage includes parenchymal haemorrhages after CNS infarction, types I and II - see “Haemorrhagic Infarction”.

Definition of stroke caused by intracerebral haemorrhage: Rapidly developing clinical signs of neurological dysfunction attributable to a focal collection of blood within the brain parenchyma or ventricular system that is not caused by trauma.

Protocol
 Trial ID:NN7415-4255
 UTN:U1111-1179-3872
 EudraCT no.:2016-000614-29

~~CONFIDENTIAL~~

Date: 28 August 2018
 Version: 5.0
 Status: Final
 Page: 87 of 127

Novo Nordisk

Definition of silent cerebral haemorrhage: A focal collection of chronic blood products within the brain parenchyma, subarachnoid space, or ventricular system on neuroimaging or neuropathological examination that is not caused by trauma and without a history of acute neurological dysfunction attributable to the lesion.

Definition of subarachnoid haemorrhage: Bleeding into the subarachnoid space (the space between the arachnoid membrane and the pia mater of the brain or spinal cord).

Definition of stroke caused by subarachnoid haemorrhage: Rapidly developing signs of neurological dysfunction and/or headache because of bleeding into the subarachnoid space (the space between the arachnoid membrane and the pia mater of the brain or spinal cord), which is not caused by trauma.

Definition of stroke caused by cerebral venous thrombosis: Infarction or haemorrhage in the brain, spinal cord, or retina because of thrombosis of a cerebral venous structure. Symptoms or signs caused by reversible edema without infarction or haemorrhage do not qualify as stroke.

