Definition of stroke, not otherwise specified: An episode of acute neurological dysfunction presumed to be caused by ischemia or haemorrhage, persisting ≥ 24 hours or until death, but without sufficient evidence to be classified as one of the above.

Definition of a Transient Ischemic Attack: The definition of Transient Ischemic Attack is according to the American Heart Association/American Stroke Association. Accordingly: a Transient ischemic attack (TIA) is a transient episode of neurological dysfunction caused by focal brain, spinal cord, or retinal ischemia, without acute infarction²⁷.

E) Definition of deep vein thrombosis:

The “Clinical Practice Guideline from the American Academy of Family Physicians and the American College of Physicians” on diagnosis of venous thromboembolism recommends ultrasound scanning for patients with intermediate or high pre-test probability of deep vein thrombosis (DVT) in the lower extremities²⁵. Accordingly, venous thrombosis should be demonstrated by compression ultrasound, duplex ultrasound, colour Doppler imaging or venography (phlebography).

F) Definition of other clinically significant thromboembolic events:

Signs or suspicion of a clinically significant thromboembolic event (e.g. visceral arterial embolus/thrombus, extremity arterial embolus/thrombus, or portal venous thrombosis). Superficial thrombophlebitis is not considered a clinically significant thromboembolic event unless evaluated as such by the investigator.

Protocol
 Trial ID:NN7415-4255
 UTN:U1111-1179-3872
 EudraCT no.:2016-000614-29

~~CONFIDENTIAL~~

Date: 28 August 2018
 Version: 5.0
 Status: Final
 Page: 88 of 127

Novo Nordisk

G) Definition of peripheral artery occlusion:

Clinical signs of acute arterial occlusion verified by ankle-brachial index (ABI) test, Doppler and ultrasound (Duplex) imaging, computerised tomographic angiography, magnetic resonance angiogram (MRA), or conventional angiography. The 2011 American College of Cardiology Foundation/American Heart Association Focused Update of the Guideline for the Management of Patients With Peripheral Artery Disease could serve as a reference for the diagnosis of lower extremity peripheral artery disease²⁸

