12.3 Follow-up of adverse events

The investigator must record follow-up information by updating the forms in the eCRF.

Follow-up information must be reported to Novo Nordisk according to the following:

- **SAEs:** All SAEs must be followed until the outcome of the event is “recovered/resolved”, “recovered/resolved with sequelae” or “fatal”, and until all queries have been resolved. Cases of chronic conditions, cancer or AEs ongoing at time of death (where death is due to another AE) may be closed with the outcome “recovering/resolving” or “not recovered/not resolved”. Cases can be closed with the outcome of “recovering/resolving” when the patient has completed the follow-up period and is expected by the investigator to recover.

The SAE follow-up information should only include new (e.g. corrections or additional) information and must be reported **within 24 hours** of the investigator’s first knowledge of the information. This is also the case for previously non-serious AEs which subsequently become SAEs.

Protocol
 Trial ID:NN7415-4255
 UTN:U1111-1179-3872
 EudraCT no.:2016-000614-29

~~CONFIDENTIAL~~

Date:	28 August 2018	Novo Nordisk
Version:	5.0	
Status:	Final	
Page:	92 of 127	

- **Non-serious AEs:** Non-serious AEs must be followed until the outcome of the event is “recovering/resolving”, “recovered/resolved” or “recovered/resolved with sequelae” or until the end of the follow-up period stated in the protocol, whichever comes first, and until all queries related to these AEs have been resolved. Cases of chronic conditions, cancer or AEs ongoing at time of death (where death is due to another AE) may be closed with the outcome “recovering/resolving” or “not recovered/not resolved”. Cases can be closed with the outcome of “recovering/resolving” when the patient has completed the follow-up period and is expected by the investigator to recover.
- **Non-serious AEs fulfilling the AESI criteria:** Non-serious AE fulfilling the AESI criteria must be followed as specified for non-serious AE. Follow-up information on AESIs should only include new (e.g. corrections or additional) information and must be reported **within 14 calendar days** of the investigator’s first knowledge of the information. This is also the case for previously reported non-serious AEs which subsequently fulfil the AESI criteria.

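### A clinically significant thromboembolic event or DIC meets a 12.7 hold criterion, but if judged non-serious it need not be reported for 14 days

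*Protocol*

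**What the plan says.** Section 12.7 lists criteria, any one of which halts further enrolment across the clinical trial programme and leads to an urgent safety committee meeting. A significant thromboembolic event and an event of DIC each stand there as single-event criteria, with nothing said about seriousness. Patients already on treatment may go on dosing while the committee evaluates.

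Section 12.1.6 defines the events of special interest: "In this trial, the following AEs fulfil the AESI criteria", and the list that follows contains only thromboembolic events, DIC among them. Section 12.2 sets aside seriousness when it chooses the forms: "AESIs regardless of the seriousness, must be reported using the AE form and safety information form". It does not do so when it sets the clock. For an SAE it requires "The AE form within 24 hours and the safety information form within 5 calendar days"; for a non-serious AESI it requires "The AE form and safety information form within 14 calendar days".

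Whether the event is an SAE is settled in 12.1.2. An event that is not fatal, life-threatening, disabling or a cause of hospitalisation becomes an SAE only if medical judgement holds that "they may jeopardise the patient and may require medical or surgical intervention" to avert one of the listed outcomes. The same section lists events that are always SAEs. That list contains suspected transmission of infectious agents and the Hy's law liver pattern, and neither thromboembolic events nor DIC.

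**The concern.** A rule that acts on one event can act only once the sponsor knows of it. Section 12.7 treats a significant thromboembolic event or DIC as urgent, and 18.1 names thromboembolism as a potential risk of the drug. Yet 12.2 leaves the reporting speed of that event to the investigator's view of seriousness. If the view is non-serious, the permitted delay is 14 days. During that time other patients dose daily, and may be escalated under 5.3.1, before anyone has to tell the committee. No event is lost from the safety data and no endpoint or analysis is affected; the question is when the safety decision can be taken.

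**Working it through.** No power or alpha figure is involved, so the check sets the sections side by side and compares the time limits.

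1. **Does 12.7 require seriousness?** Not in its words. The thromboembolic and DIC criteria carry no such condition, while another criterion in the same list is expressly limited to SAEs.

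2. **Does 12.1.2 supply it?** Not by rule. The always-SAE list omits both event types, and the important-medical-event route is a matter of judgement.

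3. **Can an event be a 12.7 trigger and a non-serious AESI?** Yes, as the text stands. A deep vein thrombosis shown by ultrasound and managed without admission meets 12.1.6 E, and could be judged significant but not serious. A silent infarction meets 12.1.6 D, which asks for "Imaging or neuropathological evidence of CNS infarction, without a history of acute neurological dysfunction attributable to the lesion".

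4. **What do the limits differ by?** All run from the investigator's first knowledge (12.2).

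| Form | SAE | Non-serious AESI | Difference |
|---|---|---|---|
| AE form | 24 hours (1 day) | 14 days | 14 − 1 = 13 days |
| Safety information form | 5 days | 14 days | 14 − 5 = 9 days |

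5. **Does any other section set a faster binding route?** None was found.
   - 13.2 states only a preference for eCRF entry within 5 days of the visit.
   - 8.1.4 requires a treatment discontinuation session in the IWRS, with no deadline.
   - 8.2.3 requires the monitor to be told if a medication change affects eligibility to continue, with no deadline.
   - Figure 12-1, to which 12.2 refers for timelines, is not reproduced in the available text and could not be checked.

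6. **Does the follow-up limit add to the problem?** Section 12.3 says: "Follow-up information on AESIs should only include new (e.g. corrections or additional) information and must be reported within 14 calendar days". Follow-up on an event already reported does not delay the hold, because the first report has by then informed the sponsor. The same 14 days do also cover a previously reported non-serious AE that only later meets the AESI definition.

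**The case against.** The strongest counter-argument is that the two event sets differ. The AESI class is wider than the 12.7 triggers: it takes in laboratory indications of thrombosis and is not a closed list. The 14-day tier therefore has a proper use for minor events. Section 12.1.6 F supports this: "Superficial thrombophlebitis is not considered a clinically significant thromboembolic event unless evaluated as such by the investigator". A reader might infer that the whole tier is wrong and that every AESI belongs on the 24-hour clock. The documents do not support that; only events meeting a hold criterion need to move.

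Second, 12.7 speaks of two or more *other* related SAEs, which suggests that the authors took the preceding triggers to be SAEs already. On that reading the 24-hour limit applies to all of them. This has some weight, and it means one should not say that 12.7 expressly covers non-serious events. It is an implication only, and 12.1.2 does not carry it through.

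Third, the group is small. An event significant enough to halt a programme will usually be an important medical event, and note d in 12.1.2 already counts intensive treatment at home. The silent-infarct example is an incidental finding, since the visit descriptions include no routine brain imaging. All of this stands.

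Fourth, the consequences are limited. The affected patient must stop under 6.4. Escalation of others already requires a review of the clinical picture and coagulation results (5.3.1). A full fortnight's silence is also unlikely: 5.3.3 prohibits heparin, vitamin K antagonists and direct oral anticoagulants, so treating a thrombosis would probably bring the monitor in through 8.2.3. These points make the delay less likely and less costly, but none sets a deadline.

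**Conclusion.** The gap is real and narrow. For a clinically significant thromboembolic event or DIC judged non-serious, the protocol permits the AE form up to 13 days later and the safety information form up to 9 days later than for an SAE. The urgent meeting in 12.7 can be delayed by the same amount. This rests on reading 12.7 as written, with no seriousness condition, and on the unseen Figure 12-1 matching the text. The documents give no frequency for such events; few are expected.

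Three larger claims might be inferred and are not supported.

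- **That 12.2 and 12.7 contradict each other.** They do not; both can be followed, but the hold may start late.
- **That prompt reporting would stop other patients' dosing.** Section 12.7 allows dosing during the evaluation, so what is delayed is the committee's decision.
- **That more patients would be enrolled in this trial during the delay.** At the planned pace, 33 patients over the 122 days from 16 August to 16 December 2017, the figure would be 33/122 × 14 = 3.8. But that recruitment period had closed before version 5.0 of 28 August 2018. The hold now matters for the wider programme, whose recruitment status is not shown.

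This is a cheap improvement to a safety procedure, not a defect in the trial's inference.

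**What to change.** Make one of two changes.

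- In 12.1.2, add clinically significant thromboembolic events and DIC to the events always reported as SAEs.
- Or, in 12.2, state that any event meeting a 12.7 hold criterion is reported on the SAE timeline regardless of seriousness: AE form within 24 hours and safety information form within 5 calendar days of the investigator's first knowledge.

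Keep the 14-day limit for other non-serious AESIs, such as superficial thrombophlebitis that the investigator does not consider significant. Figure 12-1 should be aligned if it shows the same limits.

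The cost is one line of text, with no new form or assessment. The downside is a few additional urgent reports, which limiting the rule to clinically significant events and DIC keeps small.
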